8.2.2.1. Local Reactions

For the first 7 days following each study vaccination (Days 1 through 7, where Day 1 is the day of vaccination), the participants will be asked to assess redness, swelling, and pain at the 20vPnC injection site and to record the symptoms in the e-diary in the evening. Redness and swelling will be measured and recorded in measuring device (caliper) units (range: 1 to 21) and then categorized during analysis as mild, moderate, or severe based on the grading scale in Table 1. Measuring device units can be converted to centimeters according to the following scale: 1 measuring device unit = 0.5 cm. Pain at the vaccine injection site will be assessed by the participant as mild, moderate, or severe according to the grading scale in Table 1. The participant will be prompted to contact the investigator if he/she experiences a severe (Grade 3 or above) local reaction to assess the reaction and perform an unscheduled assessment or visit as appropriate.

Only an investigator is able to classify a participant's local reaction as Grade 4, after physical examination of the participant or documentation from another medically qualified source (eg, emergency room or hospital record). If a participant experiences a Grade 4 local reaction, the investigator must immediately notify the sponsor. Site staff will educate the participants regarding signs and symptoms that would prompt site contact. Grade 4 reactions will be collected as an AE on the CRF. The event will be graded using the AE severity grading scale ([Section 10.2](#)).

The procedure for notification of the sponsor is provided in the ISF or equivalent.

Table 1. Grading Scales for Local Reactions

	Mild Grade 1	Moderate Grade 2	Severe Grade 3^a	Grade 4^b
Redness	5 to 10 measuring device units = >2.0 to 5.0 cm	11 to 20 measuring device units = >5.0 to 10.0 cm	>20 measuring device units = >10.0 cm	Necrosis or exfoliative dermatitis
Swelling	5 to 10 measuring device units = >2.0 to 5.0 cm	11 to 20 measuring device units = >5.0 to 10.0 cm	>20 measuring device units = >10.0 cm	Necrosis

Table 1. Grading Scales for Local Reactions

	Mild Grade 1	Moderate Grade 2	Severe Grade 3^a	Grade 4^b
Pain at injection site	Does not interfere with activity	Interferes with activity	Prevents daily activity ^c	Emergency room visit or hospitalization for severe injection site pain

Abbreviation: CRF = case report form.

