9.3.4. Primary Endpoint(s)/Estimand(s) Analysis

Objectives	Endpoint and Estimand	Statistics
Safety	
 Proportions of participants (by age cohort) with local reactions (redness, swelling, and pain at the injection site) within 7 days after vaccination. Proportions of participants (by age cohort) with systemic events (fever, headache, fatigue, muscle pain, and joint pain) within 7 days after vaccination. Proportions of participants (by age cohort) with AEs within 1 month after vaccination. Proportions of participants (by age cohort) with SAEs within 1 month after vaccination. 	Descriptive summary statistics for participants with each local reaction/systemic event by intensity level.
		Descriptive summary statistics.
		Descriptive summary statistics.
		Descriptive summary statistics.

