- The investigator will attempt to establish a diagnosis of the event based on signs, symptoms, and/or other clinical information. Whenever possible, the diagnosis (not the individual signs/symptoms) will be documented as the AE or SAE.

Assessment of Intensity

The investigator will make an assessment of intensity for each AE and SAE reported during the study and assign it to 1 of the following categories:

- Mild: Asymptomatic or mild symptoms; clinical or diagnostic observations only; intervention not indicated.
- Moderate: Minimal, local or noninvasive intervention indicated; limiting age-appropriate instrumental ADL. Instrumental ADL refers to preparing meals, shopping for groceries or clothes, using the telephone, managing money, etc.
- Severe: Severe or medically significant but not immediately life-threatening; hospitalization or prolongation of hospitalization indicated; disabling, limiting self care ADL. Self care ADL refers to bathing, dressing and undressing, feeding self, using the toilet, taking medications, and not bedridden.

An event is defined as "serious" when it meets at least 1 of the predefined outcomes as described in the definition of an SAE, NOT when it is rated as severe.

GRADE	If required on the AE page of the CRF, the investigator will use the adjectives MILD, MODERATE, SEVERE to describe the maximum intensity of the AE. For purposes of consistency, these intensity grades are defined as follows:	
1	MILD	Does not interfere with participant's usual function.
2	MODERATE	Interferes to some extent with participant's usual function.

3	SEVERE	Interferes significantly with participant's usual function.
---	--------	---

Assessment of Causality

- The investigator is obligated to assess the relationship between study intervention and each occurrence of each AE or SAE. The investigator will use clinical judgment to determine the relationship.
- A “reasonable possibility” of a relationship conveys that there are facts, evidence, and/or arguments to suggest a causal relationship, rather than a relationship cannot be ruled out.
- Alternative causes, such as underlying disease(s), concomitant therapy, and other risk factors, as well as the temporal relationship of the event to study intervention administration, will be considered and investigated.
- The investigator will also consult the IB and/or product information, for marketed products, in his/her assessment.

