3.1.1. Local Reactions

The local reactions assessed and reported in the e-diary are redness, swelling, and pain at the injection site, from Day 1 through Day 7, where Day 1 is the day of vaccination. This section describes derivations with details for the assessment of local reactions: severity level, duration, and onset day.

Severity and Maximum Severity

Redness and swelling will be measured and recorded in measuring device (caliper) units (range: 1 to 21), and then categorized during analysis as mild, moderate, or severe based on the grading scale in [Table 3](#). Measuring device units can be converted to centimeters according to the following scale: 1 measuring device unit = 0.5 cm. Pain at the vaccine injection site will be assessed by the participant as mild, moderate, or severe according to the grading scale in [Table 3](#).

Table 3. Grading Scales for Local Reactions in Study Participants

Local Reaction	GRADE 1 Mild	GRADE 2 Moderate	GRADE 3 ^a Severe	GRADE 4 ^b
Redness	5 to 10 measuring device units = >2.0 to 5.0 cm	11 to 20 measuring device units = >5.0 to 10.0 cm	>20 measuring device units = >10.0 cm	Necrosis or exfoliative dermatitis
Swelling	5 to 10 measuring device units = >2.0 to 5.0 cm	11 to 20 measuring device units = >5.0 to 10.0 cm	>20 measuring device units = >10.0 cm	Necrosis
Pain at injection site	Does not interfere with activity	Interferes with activity	Prevents daily activity ^c	Emergency room visit or hospitalization for severe pain at injection site

Note: If the size of the redness and/or swelling falls between 2 measuring device units, the higher measuring device unit number will be recorded in the e-diary.

- a. Participants experiencing Grade 3 local reactions are required to contact the investigator site. In the event that the participant does not call, the investigator will call the participant.
- b. Grade 4 assessment should be made by the investigator; Grade 4 local reactions will not be collected in the e-diary but will be collected as AEs on the CRF, and intensity should be graded using the AE intensity grading scale in Section 10.2.3 of the protocol.
- c. Prevents daily activity, eg, results in missed days of work or is otherwise incapacitating.

For each local reaction, the maximum severity grade will be derived for the e-diary collection period (Day 1 through Day 7, where Day 1 is the day of vaccination) as follows:

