Maximum severity grade = highest grade (maximum severity) within 7 days after vaccination (Day 1 through Day 7) among severity grades reported for that local reaction in the e-diary.

CCI

CCI

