3.1.2. Systemic Events (Systemic Event Symptoms and Fever)

The systemic events assessed and recorded in the e-diary are fever, fatigue (tiredness), headache, muscle pain, and joint pain from Day 1 through Day 7, where Day 1 is the day of vaccination. The derivations for systemic events will be handled similarly to the way local reactions are handled: severity level, duration, and onset day.

The systemic events of fatigue, headache, muscle pain, and joint pain will be assessed by the participant as mild, moderate, or severe according to the grading scale in Table 4. Grade 4 systemic events will not be collected in the e-diary but will be collected as an AE on the CRF. The event will be graded using the AE severity grading scale.

Table 4. Grading Scales for Systemic Events

Systemic Event	GRADE 1 Mild	GRADE 2 Moderate	GRADE 3 Severe ^a	GRADE 4 ^b
Fatigue (tiredness)	Does not interfere with activity	Some interference with activity	Prevents daily routine activity	Emergency room visit or hospitalization for severe fatigue
Headache	Does not interfere with activity	Some interference with activity	Prevents daily routine activity	Emergency room visit or hospitalization for severe headache
Muscle pain	Does not interfere with activity	Some interference with activity	Prevents daily routine activity	Emergency room visit or hospitalization for severe muscle pain
Joint pain	Does not interfere with activity	Some interference with activity	Prevents daily routine activity	Emergency room visit or hospitalization for severe joint pain

a. Prevents daily routine activity, eg, results in missed days of work or is otherwise incapacitating; includes use of narcotics for analgesia.

b. Grade 4 assessment should be made by the investigator. Grade 4 systemic events will not be collected in the e-diary but will be collected in the CRF. The severity of the systemic event should be graded using the AE severity grading scale as per the protocol Section 10.2.

Fever

Temperatures recorded in degrees Fahrenheit will be programmatically converted to degrees Celsius first for reporting. Fever will be grouped into ranges for the analysis according to Table 5.

Table 5. Ranges for Fever

≥38.0°C to 38.4°C
>38.4°C to 38.9°C
>38.9°C to 40.0°C ^a
>40.0°C

Note: Fever is defined as a temperature of ≥38.0°C.

a. Participants reporting a fever >39.0°C will be prompted to contact the study site.

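### On the visible text, maximum severity of prompted events comes from e-diary grades only, so the primary severity tables stop at Grade 3 although Grade 4 is defined

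*SAP*

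**What the plan says.** SAP 3.1.1 derives maximum severity over Days 1 to 7 as the highest grade "among severity grades reported for that local reaction in the e-diary". Redness and swelling are recorded in caliper units and "then categorized during analysis as mild, moderate, or severe based on the grading scale in" Table 3; pain is rated by the participant on the same three levels. For systemic events, SAP 3.1.2 states: "The derivations for systemic events will be handled similarly to the way local reactions are handled: severity level, duration, and onset day".

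SAP Tables 3 and 4 also define Grade 4 for redness, swelling, injection site pain, fatigue, headache, muscle pain and joint pain. Fever is different: Table 5 gives temperature ranges and no Grade 4. On where Grade 4 is recorded, the SAP says "Grade 4 local reactions will not be collected in the e-diary but will be collected as AEs on the CRF" and "Grade 4 systemic events will not be collected in the e-diary but will be collected as an AE on the CRF". The protocol agrees (8.2.2.1, 8.2.2.2) and adds "If a participant experiences a Grade 4 local reaction, the investigator must immediately notify the sponsor", with a matching rule for systemic events. Severity is then graded on the AE scale of protocol 10.2.3, where "the investigator will use the adjectives MILD, MODERATE, SEVERE to describe the maximum intensity of the AE".

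SAP 6.1.1.1 and 6.1.2.1 present the primary prompted-event results by maximum severity, in the safety population with any e-diary data. Protocol 9.3.4 describes these results as "Descriptive summary statistics for participants with each local reaction/systemic event by intensity level".

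**The concern.** The grading tables have four levels, but the derivation reads a source that can hold only three. A participant with a Grade 4 event is therefore tabulated at whatever the diary holds, and the worst prompted events look milder than the investigator judged them to be.

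The study is descriptive and its primary objective is the safety profile, so the severity tables are a main result. If a Grade 4 event occurs, they understate it. If none occurs, they cannot report zero Grade 4 events with an upper confidence limit, because the diary could never have shown one. A Grade 4 row filled with zeros from the diary would be worse than no row: it would look like an observed zero.

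**Working it through.** No figure in the plan depends on this rule, so the check is mainly a trace from data source to table.

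**Trace**

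1. Levels defined: Grades 1 to 4 for three local reactions (SAP Table 3) and four systemic symptoms (SAP Table 4).
2. Levels the e-diary can hold: Grades 1 to 3. Both documents send Grade 4 to the AE page of the CRF.
3. Source for maximum severity: the e-diary only (SAP 3.1.1, carried to 3.1.2).
4. Primary tables: by that maximum severity (SAP 6.1.1.1, 6.1.2.1). The highest attainable level is therefore Grade 3.
5. Other visible routes:
   - The AE severity scale has three levels, so it cannot identify Grade 4.
   - The AE table is by system organ class and preferred term (SAP 6.1.3.1).
   - SAP 6.1.4.2 mentions AE listings, with no Grade 4 marker visible.
   - The local-reaction sensitivity analysis adds back e-diary errors, not CRF events.
   - Protocol 8.10 has injection site pain graded at an unscheduled visit, with a CRF page for that visit, but the derivation does not use that page.

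**Where a Grade 4 participant would appear**

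- Pain and the four systemic symptoms: Grade 4 means an emergency room visit or hospitalization for a severe symptom, so a diary kept that day would plausibly show Grade 3.
- Redness and swelling: the diary grade depends on size alone. Necrosis within an area of 5 to 10 units would be tabulated as mild.
- Diary data exist but no grade was entered for that event: shown without the event.
- No diary data at all: outside the denominator (SAP 4), so not shown as event-free.

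**Size per case**

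Inputs are 200 participants per cohort and 400 overall (protocol 9.5). Intervals are Clopper-Pearson, as planned in SAP 5.2.1. Assume first that everyone reports diary data.

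- One case in a cohort: 1/200 = 0.50% (95% CI 0.01% to 2.8%).
- One case overall: 1/400 = 0.25% (0.01% to 1.4%).
- If 90% report diary data (assumption): 1/180 = 0.56% and 1/360 = 0.28%.

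**A properly ascertained zero**

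For zero events the exact upper limit is 1 − 0.025^(1/n).

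- n = 200: 1 − 0.025^(1/200) = 1.8%.
- n = 400: 1 − 0.025^(1/400) = 0.9%.

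**Which denominator to use**

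SAP 6.5.2.3 foresees participants who transmit no diary. Suppose they entered the severity table only when they had a Grade 4 event. With d the share reporting diary data and p the Grade 4 rate, the expected percentage would be p/(d + (1 − d)p). With p = 0.5% and d = 90% (both assumptions) this is 0.005/(0.9 + 0.1 × 0.005) = 0.555%, a ratio of 1.11 to the true rate. With d = 95% the ratio is 1.05, and with d = 80% it is 1.25. The e-diary denominator should therefore stay as it is, with participants who have no diary data covered by a separate count.

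**The case against.** The strongest reply is that the routing is intended. Protocol and SAP agree that the investigator assigns Grade 4, that it stays out of the diary, and that it is handled as an AE. On that view the analysed intensity levels are three by design, and protocol 9.3.4 does not promise a Grade 4 row. The events also remain in the primary results: AEs and SAEs are primary endpoints, tabulated with confidence intervals on the full safety population, and the sponsor is notified of every Grade 4 event. Finally, redactions follow the derivation in SAP 3.1.1 and the main analyses in 6.1.1 to 6.1.3, which is where a Grade 4 rule could sit.

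Much of this stands. A reader might infer that the documents contradict each other, or that Grade 4 events drop out of the primary safety results. Neither is supported: collection is consistent, and the AE and SAE percentages are unaffected. It would also be too strict to say that Grade 4 is recorded only as an AE, given the pain grading in protocol 8.10. Nor may a rule that could lie under a redaction be called absent from the plan.

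What the reply does not answer is the display. A count by preferred term does not show which events were Grade 4, and the visible rule for maximum severity still places such a participant at a lower grade in the severity table.

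**Conclusion.** The point holds on the visible text as a minor reporting gap. The primary tables by maximum severity stop at Grade 3 for local reactions and for fatigue, headache, muscle pain and joint pain, and no visible output identifies Grade 4 events as such. Fever is not affected.

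The effect is confined to the prompted-event severity tables. The documents give no Grade 4 rate, so no expected effect can be derived; it is probably very small. Each case would be 0.5 percentage points of a cohort or 0.25 overall if all participants report diary data. The conclusion assumes that redacted text contains no rule for Grade 4. If it does, the gap closes.

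**What to change.** In SAP 3.1.1 and 3.1.2, for participants with e-diary data, define maximum severity as the higher of (i) the Day 1 to 7 e-diary grades and (ii) any investigator-confirmed Grade 4 prompted local reaction or systemic symptom on the CRF with onset on Days 1 to 7. Add a Grade 4 row to the tables in 6.1.1 and 6.1.2, and leave the e-diary denominator and the fever ranges unchanged.

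Report separately, by cohort and overall, the number and percentage (exact 95% CI) of participants with any Grade 4 prompted event, on the full safety population. Keep the Grade 4 classification in the analysis data, and footnote that these events also appear in the AE tables. If redacted text already does this, a cross-reference is enough.

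The cost is SAP wording, minor programming and a Grade 4 identifier if none exists. No grading rule, data collection route, visit or sample size changes. The downside is that one event appears in two displays, which the footnote explains.

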3.1.2. Systemic Events (Systemic Event Symptoms and Fever)

The systemic events assessed and recorded in the e-diary are fever, fatigue (tiredness), headache, muscle pain, and joint pain from Day 1 through Day 7, where Day 1 is the day of vaccination. The derivations for systemic events will be handled similarly to the way local reactions are handled: severity level, duration, and onset day.

The systemic events of fatigue, headache, muscle pain, and joint pain will be assessed by the participant as mild, moderate, or severe according to the grading scale in Table 4. Grade 4 systemic events will not be collected in the e-diary but will be collected as an AE on the CRF. The event will be graded using the AE severity grading scale.

Table 4. Grading Scales for Systemic Events

Systemic Event	GRADE 1 Mild	GRADE 2 Moderate	GRADE 3 Severe ^a	GRADE 4 ^b
Fatigue (tiredness)	Does not interfere with activity	Some interference with activity	Prevents daily routine activity	Emergency room visit or hospitalization for severe fatigue
Headache	Does not interfere with activity	Some interference with activity	Prevents daily routine activity	Emergency room visit or hospitalization for severe headache
Muscle pain	Does not interfere with activity	Some interference with activity	Prevents daily routine activity	Emergency room visit or hospitalization for severe muscle pain
Joint pain	Does not interfere with activity	Some interference with activity	Prevents daily routine activity	Emergency room visit or hospitalization for severe joint pain

a. Prevents daily routine activity, eg, results in missed days of work or is otherwise incapacitating; includes use of narcotics for analgesia.

b. Grade 4 assessment should be made by the investigator. Grade 4 systemic events will not be collected in the e-diary but will be collected in the CRF. The severity of the systemic event should be graded using the AE severity grading scale as per the protocol Section 10.2.

Fever

Temperatures recorded in degrees Fahrenheit will be programmatically converted to degrees Celsius first for reporting. Fever will be grouped into ranges for the analysis according to Table 5.

Table 5. Ranges for Fever

≥38.0°C to 38.4°C
>38.4°C to 38.9°C
>38.9°C to 40.0°C ^a
>40.0°C

Note: Fever is defined as a temperature of ≥38.0°C.

a. Participants reporting a fever >39.0°C will be prompted to contact the study site.

3.1.3. Adverse Events

AEs will be categorized according to MedDRA terms. AEs will be assessed from the time of informed consent through 1 month after vaccination.

AE reporting will be based on the specific reporting period. Missing AE start dates will be imputed following the Pfizer data standard rules as described in [Section 5.3](#).

3.1.4. Serious Adverse Events

SAEs will be categorized according to MedDRA terms. SAEs will be collected from the time of informed consent through the end of the study (1 month after vaccination).

3.2. Secondary Endpoint

[figure not shown]
- Pneumococcal serotype-specific OPA titers before and 1 month after vaccination.

OPA titers for each pneumococcal serotype will be determined for each participant in the immunogenicity subset (approximately 50 participants in each age cohort) using the Luminex assay and Pfizer's OPA assay, both before vaccination and 1 month after vaccination. Fold changes in OPA titers will be calculated for each participant by taking the ratio of OPA titers 1 month after vaccination to before vaccination.

CCI

CCI

3.4. Baseline Variables

Measurements or samples collected before vaccination are considered the baseline data for the assessments.

3.4.1. Demographics and Medical History

The demographic variables are age at vaccination (in years), sex (male or female), race (Black/African American, American Indian or Alaskan native, Asian, Native Hawaiian or other Pacific Islander, White, not reported, and unknown), ethnicity (Hispanic/Latino or of Spanish origin and non-Hispanic/non-Latino), height, weight, and racial designation (Indian Subcontinent Asian, Southeast Asian, Far East Asian, Japanese, Korean, Chinese, Taiwanese, and others).

Age at vaccination will be derived in years based on the participant's birthday. For example, if the vaccination date is 1 day before the participant's 18th birthday, the participant will be considered 17 years old. For participants who completed Visit 1 but did not receive the vaccine, the enrollment date will be used in place of the date of vaccination for the age calculation. If the Visit 1 date is also missing, then the informed consent date will be used for age calculation.

In cases where more than 1 category is selected for race, the participant will be counted under the category "multiracial" for analysis.

Medical history will be categorized according to MedDRA.

3.4.2. E-Diary Transmission

An e-diary will be considered transmitted if any data for the local reactions and systemic events are present for any day.

